- 4) motor symptoms expected to interfere with scanning
- 5) contraindications to TMS:
 - history of seizures or status epilepticus,
 - unstable coronary artery disease
 - hydrocephalus
 - implantable electrodes, cerebral spinal fluid shunts, skull plates or other intracranial metal
 - medical devices including pacemakers or other implantable stimulators or pumps
 - subjects taking medications known to lower seizure threshold
 - pregnancy

In order to complete recruitment including consent screen failures, drop-outs and unusable datasets we request the capacity to recruit up to 150 participants.

C. Study Design and Research Methods

Aim 1 Rationale and Design: Even while not engaged in a task the brain exhibits spatially and temporally organized patterns of activity.⁸⁴ The past 15 years has seen remarkable progress in understanding these intrinsic functional networks (also termed resting-state networks) in both health and disease.⁸⁵ Intrinsic networks are consistent within and across individuals, correlate with behavioral and clinical outcomes, and can be analyzed with graph theory measures to define global and local aspects of network organization.⁵⁹ MEG can be used to identify multiple intrinsic networks similar to fMRI but with additional information regarding the power spectra of connections.^{86, 87} Importantly, MEG measures of intrinsic activity can sensitively discriminate AD from other neurological disorders and correlate with cognitive function in both AD and multiple sclerosis.^{40, 47, 64} Prior studies of PD suggest changes in cortical connectivity may be associated with dementia but did not define network organization using graph theory.⁸⁸ Our *objective* for this experiment is to determine whether graph theory measures of intrinsic MEG activity correlate with cognitive dysfunction in PD. We *hypothesize* that loss of small-world architecture contributes to cognitive dysfunction in PD through loss of local efficiency and increased randomness. To test this hypothesis, 25 PD subjects with MCI and 25 with normal cognition will undergo neuropsychological testing and a resting MEG scan for analysis for this aim. MEG and neuropsychological testing may be done on the same day or separate days, not to exceed 1 week in between. We will use graph theory measures to model the

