relationship between network connectivity and cognitive function. The data generated by this Aim will fundamentally advance our understanding of the role of cortical physiology in PD cognitive dysfunction, will provide a modern network framework for future studies in this field and may provide insights leading to future therapeutic targets.

Aim 2 Rationale and Design: While finding group differences or clinical associations in brain connectivity using MEG will improve our understanding of the pathophysiology of PD cognitive dysfunction it is unlikely to provide sufficient discriminant ability to serve as a useful diagnostic or predictive biomarker. Machine learning algorithms offer several advantages in terms of biomarker development including: 1) Characterization of data at the level of the individual; 2) Ability to simultaneously optimize multiple features from complex datasets; and 3) Allows data to drive feature selection rather than theoretical assumptions.⁷² Support Vector Machine (SVM) is a machine learning method that works by determining the maximum separation between classes in a high dimensional space composed of the features of interest.¹¹⁹ Our *objective* for this Aim is to develop a novel state-defining biomarker for PD-MCI based on MEG measures of regional activity and network connectivity using SVM. We *hypothesize* that cognitive dysfunction in PD can be characterized through a unique combination of MEG regional and network features and optimized through SVM. To test this hypothesis, we will reanalyze the MEG data collected in Aim 1 using SVM to classify PD patients with and without MCI.

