AIM 2 Statistical Analysis and Sample Size: We will use SVM to determine what combination of MEG features yields the most robust classifier for discriminating PD with and without MCI. The principle behind SVM learning is that features of interest can be modeled in a high-dimensional feature space (see Figure 2 for a visualization of a very simple 2 feature space). SVM then uses a recursive algorithm to define a hyper-plane of select features creating the greatest distance between groups of interest.¹¹⁹ Given the large potential combination of MEG features and sensors this will be a computationally intensive but tractable SVM application. As the optimal number of features to build an SVM classifier is not known a priori, we will use a procedure called bagging-cross-validation to determine the optimal number of features and maximize the information gained from SVM in this relatively small sample size.¹²¹ This approach uses a boot-strap leave one out procedure to create $n - 1$ training sets and n test subjects, where n is the total sample size, to optimize feature number and maximize the final receiver operating curve. Given the large effect sizes seen in our pilot data and other MEG studies of PDD⁵⁸, we anticipate that our *sample size* of 45 (allowing for 5 unusable data-sets from the original 50) will allow us to create a classifier with an area under the ROC curve (AUC) of 0.95 or higher comparable to AUCs seen in other SVM applications in dementia and MCI populations with as few as 15 subjects per group.⁶⁸

AIM 3 Statistical Analysis and Sample Size: We will address our primary clinical research question by determining whether there is a significant group difference between the real and sham treated PD-MCI patients on the MDRS change following rTMS using repeated measures ANOVA. We will address our primary physiologic research question by determining whether there is a significant difference between the real and sham treated PD-MCI patients on change in MEG measures of small-worldness using a repeated measures ANOVA. Planned secondary analyses will include determining group differences in change on measures of quality of life, domain specific neuropsychological results and durability at the 28-day post-TMS time point. If cognition is improved we will use regression modeling to determine if these improvements were associated in changes

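### As written, Aim 2 tunes the classifier and maximises its ROC on the same left-out subjects, with no separate evaluation, AUC interval or chance test

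*Combined protocol and SAP*

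**What the plan says.** Section IV.C (Aim 2 Rationale and Design) explains why a classifier is wanted. Of group differences or clinical associations it says "it is unlikely to provide sufficient discriminant ability to serve as a useful diagnostic or predictive biomarker". For the data, "we will reanalyze the MEG data collected in Aim 1 using SVM to classify PD patients with and without MCI"; the Aim 1 sample is "25 PD subjects with MCI and 25 with normal cognition".

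Section IV.F (AIM 2 Statistical Analysis and Sample Size) gives the method. Because the best number of features is unknown in advance, "we will use a procedure called bagging-cross-validation to determine the optimal number of features" and to "maximize the information gained from SVM in this relatively small sample size". The procedure is a bootstrap leave-one-out scheme giving training sets and "n test subjects, where n is the total sample size, to optimize feature number and maximize the final receiver operating curve". The authors anticipate that 45 usable subjects "will allow us to create a classifier with an area under the ROC curve (AUC) of 0.95 or higher", which they call "comparable to AUCs seen in other SVM applications in dementia and MCI populations with as few as 15 subjects per group". They also cite large effects in their pilot data and in other MEG studies.

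No section describes an outer loop, a hold-out or external sample, an interval for the AUC, or a test against chance. None says whether features are ranked inside the training subjects only.

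**The concern.** Leaving a subject out protects the fit for that subject. It does not protect the choice of feature number if that choice is the one giving the best ROC over the same left-out subjects. The best of several noisy AUCs is then a selected value, and 0.50 is no longer a fair benchmark for it.

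Discrimination is the purpose of Aim 2, and section IV.G lists the biomarker among three contributions of the research. The AUC is the figure that readers will carry away. A weak classifier could be presented as promising, and a strong one would be presented without any statement of how precisely 45 subjects measure it.

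**Working it through.** **Inputs.** From the protocol: 50 − 5 = 45 subjects (IV.F), 25 per group before losses (IV.C), 248 sensors and six bands (IV.A), anticipated AUC 0.95. Assumed: a 22/23 split (range 20/25 to 25/20); 248 × 6 = 1,488 independent normal features; eight candidate feature counts (1 to 200); ranking inside each bootstrap; a linear SVM.

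**1. The plan's own figure.** 50 − 5 = 45 agrees. The 0.95 cannot be re-derived, because no null AUC, significance level, power or interval width is stated for Aim 2.

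**2. Precision at 0.95 (Hanley-McNeil).** Let A be the AUC, a = A/(2 − A) and b = 2A²/(1 + A). Then Var = [A(1 − A) + (n1 − 1)(a − A²) + (n0 − 1)(b − A²)]/(n1·n0).

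- With A = 0.95, a = 0.9048, b = 0.9256 and A² = 0.9025.
- At 22/23: Var = [0.0475 + 21 × 0.00226 + 22 × 0.02314]/506 = 0.6041/506 = 0.001194, so SE = 0.035.
- Wald: 0.95 ± 1.96 × 0.0346 gives 0.88 to 1.00 (truncated at 1).
- Logit: 2.944 ± 1.96 × 0.0346/0.0475 = 2.944 ± 1.426, which back-transforms to 0.82 to 0.99.
- Splits of 20/25 to 25/20 give SE 0.033 to 0.036.
- At 15/15, the smallest size cited in support: SE 0.042, logit interval 0.77 to 0.99.

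**3. Chance benchmark for an untuned AUC.** At A = 0.5, a = b = 1/3, so Var = [0.25 + 43 × 0.0833]/506 = 0.00758 and SE = 0.087. The 95th percentile is 0.5 + 1.645 × 0.087 = 0.64. An unbiased AUC above 0.5 + 1.96 × 0.087 = 0.67 would exclude chance, so 0.95 does so easily.

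**4. Bias of the tuned AUC.** The table shows mean estimate minus AUC on new subjects (simulation SE). There were 178 runs per setting, 89 for leave-one-out.

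| Estimate | True 0.50 | 0.80 | 0.93 | 0.99 |
|---|---|---|---|---|
| Tuned, 15 bootstraps per left-out subject | +0.037 (0.009) | −0.023 (0.008) | −0.014 (0.004) | 0.000 (0.001) |
| Tuned, 60 shared bootstraps | +0.063 (0.009) | +0.002 (0.007) | +0.001 (0.004) | +0.004 (0.001) |
| Outer loop, one pair left out | +0.006 (0.012) | −0.016 (0.009) | −0.005 (0.005) | −0.004 (0.002) |
| Outer loop, 10-fold, pooled | 0.000 (0.010) | −0.040 (0.008) | −0.032 (0.005) | −0.010 (0.002) |
| Outer loop, leave-one-out, pooled | −0.078 (0.016) | −0.079 (0.013) | −0.027 (0.007) | −0.010 (0.003) |

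Other codings of the tuned loop gave no-signal biases from +0.03 to +0.09, and +0.05 at a true AUC of 0.57, +0.04 at 0.63 and +0.01 at 0.88. At a true 0.95 the bias was −0.010 to 0.000. The null 95th percentile of the tuned AUC was 0.70 to 0.78, against 0.64 in step 3. Part of that gap is the wider spread of a cross-validated AUC (SD 0.10 to 0.14 at a fixed feature count, with 1,488 features), not bias alone. A permutation test that repeats the tuning captures both.

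**5. If features are ranked once on all 45 subjects.** With pure noise and an unbagged SVM, the best leave-one-out AUC averaged 1.00 with 1,488 features (56 runs) and 0.82 with 60 features (77 runs).

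**6. Interval.** The Hanley-McNeil logit interval placed around the tuned AUC (15-bootstrap version) covered the true AUC in 79% to 94% of runs, depending on the setting. An interval that resamples subjects and re-chooses the feature number covered 89% to 99% across both versions. At a true 0.95 it averaged 0.77 to 1.00 in the 15-bootstrap version.

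**The case against.** The strongest reply is that the protocol describes the procedure in one compressed sentence and cites a source (number 121) for it. The numbered references end at 42, so that source cannot be identified. Feature number may be chosen by bootstraps inside each training set, with the left-out subject used only for testing. That stands: a reader might infer that the plan definitely reports a selected AUC, but the text does not say outright which AUC will be reported. What remains is that the plan as written states the two purposes together and describes no separate evaluation.

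A reader might also infer that the anticipated 0.95 is an artefact of tuning. The calculations do not support this when ranking is inside each bootstrap: bias near 0.95 is about zero, and no no-signal run reached 0.95. It would be a real risk only if ranking were done once on everyone.

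A third tempting reading is that the sample is inadequate because 0.95 cannot be told from 0.90. Sampling error alone does turn a true 0.90 into an observed 0.95 or more in about 13% of samples (binormal, 22/23). But the documents set no threshold at 0.90, no decision depends on 0.95, and the authors call the sample small. The fair point is the missing statement of precision.

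Finally, nesting does not improve precision. At a true 0.95 the root mean squared error was 0.047 for the pair-based outer loop and 0.043 to 0.055 for the tuned AUC. That also stands.

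**Conclusion.** The point holds in a limited form. If the maximised AUC is the reported one, it is optimistic by about 0.03 to 0.09 with no signal and close to unbiased near 0.95. A tuned AUC of about 0.70 could be taken as better than chance when it is not. These sizes rest on the assumed 22/23 split, 1,488 independent features, eight candidate counts and ranking inside each bootstrap; the documents fix none of them. Ranking outside the training subjects would make the bias far larger.

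The precision result needs no simulation. An observed 0.95 carries a 95% interval of roughly 0.82 to 0.99 (logit) or 0.88 to 1.00 (Wald), which is clearly above chance but wide. Both gaps should be closed before Aim 2 is analysed. Aims 1 and 3 are untouched.

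**What to change.** 1. List the candidate feature counts in advance. State that features are ranked, and their number chosen, only inside training subjects.
2. Keep bagging-cross-validation as the inner tuning loop. Report the AUC from an outer loop whose subjects play no part in tuning, for example repeated stratified k-fold or leave-pair-out. Avoid a pooled plain leave-one-out outer loop, which read about 0.08 low with no signal.
3. Give that AUC a 95% interval from resampling subjects and re-tuning each time, and a label-permutation p-value that repeats the whole pipeline. The coverage in step 6 of the working was checked for the tuned AUC only, so check it for the chosen outer loop before relying on it.
4. Show the tuned AUC beside it, labelled as a tuning result, and present 0.95 as an expectation to be judged against the interval.

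The cost is one paragraph of analysis text and no new data. The nested AUC reads somewhat low (about 0.01 for pairs and 0.03 for 10-fold at a true 0.95), the interval will be wide, and precision does not improve.

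Computing depends on the feature set. With 1,488 features, one tuning loop took about 0.02 s. All 22 × 23 = 506 pairs then take about 10 s, and 1,000 permutations about 3 hours. If every directed connection enters (248 × 247 × 6 = 367,536), ranking alone took about 0.22 s per bootstrap, and 60 × 506 × 1,000 × 0.22 s is about 77 single-core days. In that case use fewer folds or permutations: 10 folds with 200 permutations needs 60 × 10 × 200 × 0.22 s, about 7 hours for ranking.

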AIM 3 Rationale and Design: rTMS can improve cognition in PD without dementia⁵², PD with depression⁸⁰, older adults¹²² and in AD¹²³ but has not been tested in PD-MCI. Given the need for improved cognitive treatments and possible differences in rTMS effects on PD-MCI pathophysiology it is important to specifically test rTMS in this population. Prior studies as well as our own pilot data suggest that rTMS modulates cortical connectivity,^{16,17} thus rTMS provides not only a potentially effective intervention but an important causal test of our associative data and theoretical link between cortical connectivity and cognitive dysfunction in PD. Our *clinical objective* for this experiment is to determine whether rTMS improves cognitive outcomes in PD-MCI. Our *mechanistic objective* is to determine whether rTMS normalizes patterns of cortical connectivity. We *hypothesize* that high-frequency bifrontal rTMS will partially normalize patterns of cortical connectivity linked to frontal nodes and will improve cognitive measures. To test this hypothesis 55 PD-MCI subjects will be randomized to a 10-day course of real or sham bifrontal high frequency rTMS. We will measure cognitive and MEG outcomes pre-treatment and on the day of the last treatment (neuropsych testing and MEG procedures may be separated by 1 day if patient is fatigued) and repeat cognitive measures 28 days post rTMS to assess the durability of cognitive changes.

TMS: TMS will be administered using a 70-mm diameter air-cooled figure-of-8 coil and SuperRapid² Magstim Stimulator. We will first define the subject's resting motor threshold (MT) by localizing the hand area of motor cortex and determining the minimal TMS amplitude needed to produce a motor-evoked potential of 50 microV on 4 of 8 trials measured by EMG over the first dorsal interosseous muscle (Biopac, Goleta, CA). Once the MT is determined, repetitive pulses will be delivered to the right and left pre-frontal cortex (Brodmann area 46) using a frameless stereotactic navigation system and the subject's MRI in Brainsight software. Depending on our preliminary results from Aim 1, we may change our target if it is evident that a particular frontal node shows high clustering within beta or theta frequency bands. This type of targeting based on functional data has been previously performed and may enhance TMS effects on intrinsic connectivity.¹⁶ Stimuli will be delivered at 20 Hz at 90% rMT for 25 trains of 30 pulses per train, inter-train

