interval of 30 seconds for a total of 750 pulses per hemisphere, which is well within the most recent international TMS safety guidelines.¹²⁹ This dose and duration of rTMS is based on physiological studies of healthy adults and treatment studies of cognition in PD and Alzheimer’s disease.^{52, 123} Side of first stimulation (left vs right hemisphere) will be counterbalanced across subjects. Sham stimulation will be delivered using a sham coil fitted with electrodes to mimic both the auditory and somatic sensation of real TMS as I have performed in prior TMS trials.¹⁹

Schedule of Procedures

	Baseline Procedures ²	← 2 weeks →			28 days post-rTMS Session 10 ¹
		rTMS Session 1 ¹	rTMS Sessions 2-9 ¹	rTMS Session 10 ¹	
Informed consent	X				
MRI (anatomical and optional functional scans)	X				
MEG	X			X ¹	
Neuropsych tests	X			X ¹	X ¹
rTMS (real or sham) ¹		X ¹	X ¹	X ¹	
Randomization to real or sham TMS ¹	X				

¹PD-MCI subjects only

²Baseline procedures to be completed within 1 week of rTMS Session 1

D. Description, Risks and Justification of Procedures and Data Collection Tools:

PD-MCI and mild dementia patients may be considered a vulnerable population due to cognitive dysfunction but are necessary to answering our research questions. We are cognizant of this issue and will carefully assess potential participant’s understanding of the study, particularly of study activities and risks. If there are any concerns on the part of the investigator or potential participant, we will require that their guardian participate in the consenting process and sign an informed consent. We will also require that PD-MCI subjects give consent, or at minimum assent if fully informed consent is not possible. Our protocol and consent forms will be approved by our local IRB before approaching any potential subjects.

After enrollment and screening assessment, PD and PD-MCI subjects will undergo neuropsychological testing, magnetoencephalography (MEG) recordings, and MRI. PD-MCI subjects will then be randomized in a 1:1 ratio to real or sham TMS groups using MAPLE 9.0 software (Waterloo, Canada). Baseline neuropsychological testing, MEG, and MRI may be performed over multiple days, but all will be completed within 1 week and within 1 week of first TMS session for PD-MCI subjects.

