All subjects will be required to wear hearing protection and will be supervised by study personnel during all aspects of this study. A neurologist will be available either in person or on-call within the building in the event of a seizure or other adverse study event. Study personnel involved in human subject interactions will be trained not only in human subjects protection but will be also BLS or ACLS certified and specifically trained in seizure safety and what to do in the event of other medical emergencies. There is a COR cart available outside of the TMS and MEG laboratories. All adverse events will be reported to the IRB within 5 days and seizures or other significant adverse events associated with TMS will additionally be reported to the FDA.

E. Potential Scientific Problems:

Prior TMS trials are often questioned regarding the adequacy of patient blinding with certain sham procedures. Our sham involves both auditory and tactile stimulation, and in fact resulted in a similar improvement in depression as real TMS in our recent trial.¹⁹ Subject retention, particularly with PD-MCI, may be difficult with 2 weeks of daily treatment. We will use similar procedures to our PD apathy rTMS trial where we maintained 100% retention. Finally, our sample size is relatively small to detect clinically significant changes. This is in part due to budgetary limitations and one goal of this trial is to serve to develop a more definitive, larger trial with longer-term follow-up. Changes in sensor location over repeated recordings may result in false attribution of brain activity

changes. To address this issue, sensors will be realigned to a common sensor array to allow repeated group level analysis in a shared brain space.¹⁰⁹

F. Data Analysis Plan:

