AIM 1 Statistical Analysis and Sample Size: To address our primary research question, Spearman correlations will be used to identify frequency spectra small-worldness measures associated with the MDRS in eyes-closed data with a false detection rate set at 0.05 to handle the issue of multiple comparisons. We will then use linear regression to determine whether small-worldness in these specified frequency bands remain associated with the MDRS when controlling for each other as well as other important covariates, namely age and motor severity. A *sample size* of 45 (allowing for 5 drop-outs and/or unusable data-sets from the original 50) will allow us to detect correlations of 0.18 or higher between our MEG features and MDRS with 80% power 0.05 significance. This is comparable to correlations of 0.19 and higher seen in other resting state MEG studies of cognition.¹¹⁵ Planned secondary analyses will parallel our primary analysis to determine whether global efficiency, nodal efficiency or degree distribution are significantly associated with MDRS in linear regression models. Exploratory analyses will assess reactivity of these measures between eyes open and closed conditions and assess whether domain specific neuropsychological test scores are associated with connectivity within networks defined by domain related nodes (e.g. occipital nodes and visuospatial tests).

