in small-worldness or other MEG features. With a total *sample size* of 50 (25 per group allowing for 5 drop-outs from original 55) we will be able to determine a between group difference of 10 points on the MDRS (assuming a SD of 13 as per prior trials and an effect size 0.77)¹²⁴ with 80% power and 0.05 significance. This sample size is comparable to prior PDD studies. For example, a study of rivastigmine in PDD detected significant change on the Mattis with only 28 subjects.¹²⁴

Exploratory Aim Statistical Analyses and Sample Size: We will address our exploratory research questions by looking at Spearman correlations or linear models of MEG and MRI measures. Power considerations are similar as for Aim 1 with detection of correlations of 0.18 or higher between our MEG and MRI features with 80% power 0.05 significance.

G. Summarize Knowledge to be Gained:

PD is the second most common neurodegenerative disease, affecting over one million Americans and dementia is the most common cause of nursing home placement in this population.^{53, 54} Our understanding of the neurobiological mechanisms of cognitive dysfunction in PD are limited and we do not have efficacious treatments. This research will address this significant public health issue in three major ways: 1) Identify abnormalities in cortical connectivity associated with cognitive dysfunction in PD; 2) Develop a MEG biomarker for cognitive dysfunction in PD; and 3) Evaluate the potential for TMS to induce durable changes in PD cognitive function and connectivity. Given the burden of dementia in this population, we feel that the minimal risks involved are justified both to individual PD and PD-MCI subjects, the larger population of PD and PD-MCI patients, and to society as a whole. Recent TMS studies using published safety guidelines suggest that the risks of TMS may be even lower than previously described. Even using conservative estimates and anticipating some discomfort from prolonged sitting and cognitive testing, we argue that this research is imperative to advance this field and ultimately to provide relief to these patients and their caregivers.

H. References:

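### Aim 3 compares arms on MDRS change without baseline MDRS as a covariate; adjusting for it would add about 0 to 10 power points (equal variances, correlation 0.95 to 0.5) and cost at most about 1

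*Combined protocol and SAP*

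**What the plan says.** Section IV.F, under Aim 3, sets the primary clinical test as the "group difference between the real and sham treated PD-MCI patients on the MDRS change following rTMS using repeated measures ANOVA". The primary physiological test has the same form: a "difference between the real and sham treated PD-MCI patients on change in MEG measures of small-worldness using a repeated measures ANOVA". Neither sentence names a covariate. Secondary analyses include "domain specific neuropsychological results and durability at the 28-day post-TMS time point".

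On timing, section IV.C states: "We will measure cognitive and MEG outcomes pre-treatment and on the day of the last treatment". Cognitive testing is repeated 28 days later. Section IV.D places baseline testing first and continues: "PD-MCI subjects will then be randomized in a 1:1 ratio to real or sham TMS groups".

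Covariates appear elsewhere. Aim 1 plans regression "controlling for each other as well as other important covariates, namely age and motor severity", and section IV.A intends the motor score as a covariate for disease severity. Baseline MDRS is not named as an adjustment variable anywhere.

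The sample-size paragraph for Aim 3 takes a 10-point difference with 25 per group, "assuming a SD of 13 as per prior trials and an effect size 0.77". It does not say whether 13 is the SD of change or of a single score.

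**The concern.** Subtracting the baseline fixes its coefficient at 1. The best coefficient is the true regression slope of the post-treatment score on baseline, which is the pre-post correlation times SDpost/SDpre. When that slope is below 1, as it is whenever the variances are equal and the correlation is below 1, a change score over-corrects and carries extra noise. ANCOVA estimates the slope from the data.

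Precision matters here. Section IV.E concedes that "our sample size is relatively small to detect clinically significant changes" and says the trial should help develop a larger one, for which the width of the interval around the effect is directly useful. Baseline MDRS is measured before randomisation, so it is a legitimate covariate that is already paid for. The planned test is not wrong; the point is that it leaves available information unused.

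**Working it through.** **Inputs from the documents (section IV.F, Aim 3):** difference 10, SD 13, 25 analysed per arm, significance 0.05, stated power 80%.

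**Assumed:** a two-sided test; two time points in the primary contrast; pre-post correlation ρ and k = SDpost/SDpre, neither of which is given. Two time points is an inference: outcomes are taken before treatment and on the last treatment day, and day 28 is secondary, but the ANOVA's time levels are not listed.

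**Step 1: the plan's own figure.** The group-by-time test with two time points is a t-test on change. With 13 as the SD of change, the noncentrality is 10 / (13 × √(2/25)) = 2.72 on 48 df. Power is 76.0% (77.6% by the normal approximation), so the stated 80% is not quite reached. The baseline for comparison is 76.0%.

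**Step 2: variances.** Let s be the SD at baseline.
- Change score: s²(1 + k² − 2kρ)
- ANCOVA residual: s²k²(1 − ρ²)
- Difference between them: s²(1 − kρ)², which is zero only when the true slope kρ equals 1.

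Estimating the slope costs one degree of freedom (48 to 47) and inflates the variance of the treatment estimate by an expected 1 + 1/(50 − 4) = 47/46 = 1.022. The variance ratio, ANCOVA to change, is therefore 1.022 × k²(1 − ρ²) / (1 + k² − 2kρ). With k = 1 it reduces to 1.022 × (1 + ρ)/2. For example, at ρ = 0.5 it is 1.022 × 0.75 = 0.766.

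**Step 3: ANCOVA power, with 13 as the SD of change (planned test 76.0%).**

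| SDpost/SDpre | ρ = 0.5 | ρ = 0.7 | ρ = 0.8 | ρ = 0.9 |
|---|---|---|---|---|
| 0.8 | 93.6% | 91.4% | 90.9% | 92.2% |
| 1.0 | 86.1% | 81.5% | 79.3% | 77.1% |
| 1.1 | 83.0% | 78.4% | 76.4% | 75.0% |
| 1.2 | 80.6% | 76.4% | 75.2% | 76.0% |

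With equal variances and ρ = 0.95, power is 76.1%. The equal-variance gains are thus about 10, 6, 3, 1 and 0 points at ρ = 0.5, 0.7, 0.8, 0.9 and 0.95.

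**Step 4: worst case.** If the true slope is exactly 1, the residual variance equals the variance of change and only the 1.022 inflation and the lost degree of freedom remain. Power is 75.0%, a loss of about 1 point. ANCOVA is less precise only for ρ above 0.957 (k = 1.0), between 0.826 and 0.954 (k = 1.1), or between 0.733 and 0.898 (k = 1.2). It is never less precise at k = 0.8 or 0.9.

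**Step 5: if 13 is the single-score SD (equal variances).** The SD of change is 13√(2(1 − ρ)) and the ANCOVA residual SD is 13√(1 − ρ²). Power goes from 76.0% to 86.1% at ρ = 0.5 and from 93.1% to 95.8% at ρ = 0.7. At ρ = 0.8 or above the gain is under 1 point.

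**Step 6: interval width (13 as the SD of change).** The 95% half-width is 7.39 points for the change score. With equal variances, ANCOVA gives 6.48, 6.89, 7.09 and 7.29 at ρ = 0.5, 0.7, 0.8 and 0.9.

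**Check by simulation** (100,000 trials per setting, equal variances, SD of change 13): the gain was 10.0 points at ρ = 0.5 and 0.1 at ρ = 0.95. Where baseline was unrelated to change, 0.9 points were lost.

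**The case against.** The planned test is valid: randomisation keeps it unbiased and its error rate is right, so this is a choice between two legitimate analyses. The size of the gain rests on inputs the documents do not give, and even its sign is not fixed. At SDpost/SDpre 1.2, the differences at ρ = 0.7, 0.8 and 0.9 are about +0.4, −0.8 and 0 points.

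Holding the SD of change at 13 while ρ rises also implies a growing raw SD. With equal variances it is 13/√(2(1 − ρ)), or 13.0, 16.8, 20.6, 29.1 and 41.1 at ρ = 0.5, 0.7, 0.8, 0.9 and 0.95. If 13 is instead the raw SD, the gain matters only at lower correlations, and low correlation is not obvious when the two tests lie about two to three weeks apart. The ANOVA might include day 28, in which case these figures do not apply directly. Nothing sizes the gain for small-worldness or the secondary outcomes. Finally, section IV.A does mention the motor score as a model covariate, so Aim 3 may not be wholly unadjusted.

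All of this stands as a limit on how much would be gained. None of it gives a reason to prefer the change score. The loss is bounded at about 1 point under either reading of the SD, and the motor score is not the baseline value of the outcome.

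**Conclusion.** The point holds as an inexpensive gain in precision, not as an error in the planned test. With 25 per arm, a 10-point difference, two-sided 0.05, two time points and equal variances, adjustment adds about 0 to 10 power points over correlations of 0.95 to 0.5. That range holds whether 13 is the SD of change or of a single score. With unequal variances and 13 as the SD of change, the tabulated results run from about 1 point lost to about 18 gained (93.6% against 76.0%). The correlation and the variance ratio are assumptions, so the benefit may turn out negligible. The change is worth making because the possible loss is small and bounded.

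**What to change.** In section IV.F, make the primary clinical analysis an ANCOVA of last-treatment-day MDRS on randomised arm and baseline MDRS, reporting the adjusted difference with its 95% confidence interval. Use the same form for small-worldness, with its own baseline value as covariate, and for secondary outcomes that have a scheduled baseline, including the day-28 cognitive comparison. Fix the wording before unblinding, so that the adjustment cannot be chosen on the results.

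The cost is a change of wording in the analysis plan, with no new data or visits. The statistical price is one degree of freedom and about 2% variance inflation; at worst, power falls from 76.0% to 75.0%.
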